7.3. Data collection

Eligible participants identified from the CMP will be assigned a pseudonymous “study key”. The study key will be sent to the other participating organisations for linkage alongside the following direct identifiers:

- Date of birth
- NHS number
- Postcode
- Sex/gender

Linkage will be performed by each participating organisation, following the principles of the NHS Digital matching algorithm. At no point will direct identifiers be sent to the co-ordinating site (Critical Care Research Group, University of Oxford).

Participating organisations performing linkage will be:

- NHS Digital
- Patient Episode Database for Wales (PEDW)
- UK Renal Registry (UKRR)
- National Institute for Cardiovascular Outcomes Research (NICOR)
- Stroke Sentinel National Audit Programme (SSNAP)

On a per patient level, the study will request 5 years of diagnostic coding data prior to ICU admission (to accurately assess prior medical co-morbidities) and 1 year post hospital discharge (to assess the outcomes of this study).

After linkage, only pseudonymous personal data will be securely transferred to the sponsor (Critical Care Research Group, University of Oxford), where it will be stored and accessed within a secure computing system that conforms to UK government Cyber Essentials Plus and NHS Digital Security Toolkit certifications. The study will also link data from the UK Obstetric Surveillance System (UKOSS) to identify patients who were pregnant at the time of ICU admission. As UKOSS does not collect direct identifiers, it will be linked to the pseudonymous data set using probabilistic matching.

Data will be combined into the final pseudonymised study dataset by researchers in the Critical Care Research Group at the University of Oxford for analysis. Analysis of the study dataset will be conducted by researchers at the University of Oxford and ICNARC, following the methods outlined in Section 11. The accompanying Data Flow Diagram outlines the exchange of confidential patient information within the study.

8. PARTICIPANT IDENTIFICATION

8.1. Study Participants

8.2. Inclusion Criteria

- Age ≥ 16 years
- Admitted to an adult, general ICU in England or Wales as an emergency (unplanned)
- Admitted to ICU for either:
 - confirmed COVID-19 between 1st January to 1st July 2020
 - without confirmed COVID-19 between 1st July 2016 and 1st July 2020

8.3. Exclusion Criteria

The participant may not enter the study if ANY of the following apply:

- Patients who died in hospital after treatment on an ICU

We chose to exclude ICU admissions after 1st July 2020 to account for a possible three-month delay in patient data being registered in HES and national audit databases. Linking data sources in March and October 2021 will maximise the chance that complete data will be available for outcomes at 180 and 365 days respectively.

9. PROTOCOL PROCEDURES

9.1. Recruitment

Participants will be recruited from general adult ICUs across England and Wales who participate in the ICNARC CMP audit. All ICUs in England and Wales have participated in the CMP audit since 2015.

9.2. Screening and Eligibility Assessment

Changes to inclusion and exclusion criteria will be made by ethical amendment only.

There will be no exceptions made regarding eligibility.

9.3. Informed Consent

We will apply for Health Research Approval (HRA), under advice from the Research Ethics Committee and the Confidentiality Advisory Group (CAG) to allow access to confidential medical records without informed or written consent (Section 251 support).

Patient Notification Strategy

As part of a similar study (the C3 study), we developed a patient notification strategy with input from the Oxford REC B ethics committee and members of the Oxford ICU Forum (a group of previous ICU patients, families, and lay members).

In common with C3, the current study:

- Uses retrospective patient data.
- At no point will any attempt be made to contact or otherwise influence the future care of any the participants.
- The data set compiled for analysis will be pseudonymised and therefore stripped of all direct identifiers.
- The study will fully implement the National Data Opt-out (DCB3058) and will therefore exclude any records related to patients who have notified the NHS of their wish for their data not to be used in research.

For the C3 study, we were advised by the ethics committee that placing posters in the relative rooms or waiting areas of the participating ICUs to notify patients of the study, “was not practical and should not therefore be used”. All members of the PPI panel agreed with the ethics committee that displaying posters would not be appropriate. However, the PPI group advised that information should be available on a study website. The group advised that the website summary should be brief and accessible, with links to the detail (such as formal privacy policy) available.

Members of the Oxford ICU patient forum were also consulted for this study (OPTIC-19) and were supportive of its approach and aims.

Opt-out

The study will fully support and implement the NHS National Opt-out. We will utilise our link to NHS Digital asking them to inform us (by pseudonymous study ID) which patients have opted out and that will be a continuous process from enrolment until the study ends. Records that are already flagged within each site as meeting the opt-out will not be extracted.

If we are informed by NHS Digital of patients completing the Opt-out after data extraction, these data will be purged and future records relating to these patients will not be extracted.

We will also purge records from the study (in the same manner) if patients contact the study directly.

We will clearly display on the website links to register for the opt-out, as well as contact details for the study team.

Your data matters

The study will openly support the ICO “Your data matters campaign” (<https://ico.org.uk/your-data-matters/>). The aim is to increase the public's trust and confidence in how their data is used and made available. We will also support the NHS implementation of this campaign that has direct relevance to the study using data for patient benefit (<https://digital.nhs.uk/services/national-data-opt-out/supporting-patients-information-and-resources>).

9.4. Enrolment

This is a non-randomised observational study. Enrolment of participants will occur through their data being present within the ICNARC CMP.

9.5. Blinding and code-breaking

There is no blinding or code-breaking in this observational study.

9.6. Description of study intervention(s), comparators and study procedures (clinical)

This is a non-interventional study.

9.7. Baseline Assessments

Not applicable

9.8. Subsequent Visits

Not applicable

9.9. Sample Handling

No additional samples will be taken during this observational study.

9.10. Early Discontinuation/Withdrawal of Participants

This is an observational study. Participants can request their data to be deleted at any time in accordance with GDPR and the trial privacy policy.

9.11. Definition of End of Study

The end of the study will be 31st July 2023.

10. SAFETY REPORTING

This is an observational study using routinely-collected retrospective data, so safety reporting is not applicable

11. STATISTICS AND ANALYSIS

11.1. Statistical Analysis Plan (SAP)

The statistical aspects of the study are summarised here with details fully described in a statistical analysis plan that will be available from the time that the last participant is recruited. The SAP will be finalised before any analysis takes place.

11.2. Description of the Statistical Methods

Primary outcome

The primary outcome will be all-cause mortality at 1 year after discharge from ICU. For patients transferred between ICUs, this will be the time of discharge from the last ICU. Dates of death will be extracted from Civil Registration (deaths).

Secondary outcomes

Secondary outcomes will be:

- All-cause mortality at 30, 60, 90 and 180 days
- Any emergency (non-elective) hospital admission
- Emergency hospital admissions for respiratory infection
- Emergency hospital admission for a venous thrombotic event (deep vein thrombosis or pulmonary embolism)
- Emergency hospital admission for a major adverse cardiac event (myocardial infarction, stroke, heart failure)
- Development of end stage renal failure treated by renal replacement therapy

Reasons for hospital admission (i.e. primary diagnosis) will be identified using the International Classification of Diseases 10th Edition (ICD- 10) codes obtained by linkage to the HES/PEDW. Where required, ICD-10 codes will be assigned to broader diagnostic groups (e.g. respiratory infections) as per the UK Summary Hospital-level Mortality Indicator (SHMI) (16).

Statistical methods

For patients treated on ICU for COVID-19 and comparator groups, we will report the unadjusted proportions/incidence of primary and secondary outcomes, along with cumulative incidence function estimates over the 1 year follow-up period. When considering secondary outcomes (and where appropriate), the cumulative incidence estimates will account for the competing risk of death. For the COVID-19 group, we will also investigate the effect of ICU admission time (i.e. early epidemic, late epidemic) as this may impact their outcomes, as treatments changed over time.

We will compare the risk of the primary and secondary outcomes between the COVID-19 and comparator groups using survival models, such as Cox proportional hazards regression models or Fine and Gray models (when death is a competing risk). We will fit both univariable models (i.e. just including the COVID-19 vs comparator group variable) and multivariable models including potential confounders.

We will also analyse the data using propensity score matching as an alternative method to account for any potential confounding associated with the COVID-19 and comparator populations. A logistic propensity score will be used to create a matched population. The following variables will be considered for inclusion in the propensity score:

- Age at discharge from hospital
- Charlson/Elixhauser comorbidity index
- Ethnicity
- Illness severity (APACHE-II or ICNARC severity score) on admission to ICU
- Days of mechanical ventilation
- Week of the year of ICU admission (to account for potential increased survival over the course of the pandemic)

As an exploratory analysis, we will examine potential prognostic factors (such as patient or ICU treatment characteristics) for the primary and secondary outcomes. We will further investigate whether some of the secondary outcomes are time-varying predictors of mortality. Latent class analysis may also be used to identify any clustering of the secondary outcomes and their severity and/or timing.

Where common patient data items are available from multiple data sources (e.g. age, gender ethnicity), we will develop a standard protocol to resolve inconsistencies. Should substantial differences remain, we will explore any effect on our results through a sensitivity analysis.

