11.4. Analysis populations

Primary group

Our primary group will be patients admitted with confirmed COVID-19 between 1st January to 1st July 2020.

Comparator groups

The primary comparator group will be patients admitted to ICU with viral or bacterial pneumonia between 1st July 2016 and 1st July 2019.

Secondary comparator groups will include:

- All emergency ICU admissions between 1st July 2016 and 1st July 2019
- All emergency ICU admissions between 1st July 2016 and 1st January 2020 where the primary diagnosis was not COVID-19
- All emergency ICU admissions between 1st January and 1st July 2020 where the primary diagnosis was not COVID-19

Pregnant patients

We will undertake a sub-group analysis in patients who were pregnant when treated for COVID-19 on ICU between 1st January and 1st July 2020.

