4.4.2. ICU admissions 1st July 2016 – 1st July 2019

All emergency ICU admissions between 1st July 2016 and 1st July 2019. The 1st July 2019 cut-off is intended to allow 6 months follow-up of all patients before the COVID-19 pandemic had opportunity to influence healthcare provision.

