4.4.3. ICU admissions 1st July 2016 – 1st January 2020

All emergency ICU admissions between 1st July 2016 and 1st January 2020 where the primary diagnosis was not COVID-19. The cohort is the same as the previous one, with an additional 5 months' of ICU admissions. To allow for admissions which are closer in time to be included, and therefore to check the robustness of analyses involving the previous cohort.

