4.4.4. Non-COVID ICU admissions 1st January 2020 – 1st July 2020

All emergency ICU admissions between 1st January 2020 and 1st July 2020 where the primary diagnosis was not COVID-19. This cohort includes patients admitted to ICU concurrently to the primary COVID-19 cohort. While this cohort will likely be small, it will possibly provide a fairer comparison of outcomes if the pandemic did affect the healthcare provision during follow-up (i.e. if there were a reduction in the number of hospital admissions for non-Covid causes during the period of the pandemic due to restrictions).

5. Analysis

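### Against the all-emergency ICU comparators, the cardiac and venous thrombotic contrasts are confounded by index diagnosis, and no planned analysis shows by how much

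*Protocol*

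**What the plan says.** **Outcomes.** Protocol 11.2 lists "Emergency hospital admission for a major adverse cardiac event (myocardial infarction, stroke, heart failure" and, separately, emergency admission for deep vein thrombosis or pulmonary embolism. SAP 5.3.2 carries both forward. Neither document restricts them to first events, sets a washout, or separates a new event from a recurrence of the index illness.

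**Comparators.** Non-COVID eligibility in protocol 8.2 is an emergency admission "without confirmed COVID-19 between 1st July 2016 and 1st July 2020", with no limit on diagnosis. The only exclusion is death in hospital. SAP 4.4.2 takes "All emergency ICU admissions between 1st July 2016 and 1st July 2019". SAP 4.4.3 and 4.4.4 add only the condition "where the primary diagnosis was not COVID-19".

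**Rank of the comparators.** Protocol 11.4 treats these groups as secondary: "The primary comparator group will be patients admitted to ICU with viral or bacterial pneumonia between 1st July 2016 and 1st July 2019". The SAP defines no pneumonia cohort, so the all-emergency cohorts are the only ones it sets up for analysis.

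**Adjustment.** SAP 5.2 supplies the covariates for both the propensity score (5.4.3) and the multivariable models (5.6). It covers demographics, Elixhauser comorbidities, length of stay, severity and organ support. It does not include the reason for ICU admission. Comorbidity comes from "5 years of diagnostic coding data prior to ICU admission" (protocol 7.3). The subgroups in SAP 5.5 and the sensitivity analysis in 5.6 do not use index diagnosis.

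**The concern.** A patient admitted to ICU with an infarction, stroke, heart failure or pulmonary embolism is likely to have a raised risk of coming back with the same condition. Such patients belong to the all-emergency cohorts by definition. COVID-19 patients enter their cohort because of COVID-19, so few should have one of these conditions as the reason for admission. The two sides can therefore differ in later cardiac or thrombotic admissions because of what brought them to ICU, even if COVID-19 itself makes no difference.

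The balance checks in SAP 5.4.3 would not reveal this, because they cover only the listed covariates. SAP 3.1 reports secondary outcomes as an effect size and 95% interval, so a confounded hazard ratio would be the reported result. A real cardiac excess after COVID-19, which the background sections give reason to look for, could be diluted or hidden.

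**Working it through.** **1. Is the index event captured anywhere?** The look-back window closes at ICU admission. Protocol 12.1 gives the reason: coding from the admission itself cannot separate complications from earlier disease. Elixhauser history can therefore pick up long-standing heart failure, but not a first infarction, stroke or embolism that caused the ICU admission. No exclusion, outcome rule, covariate, subgroup or sensitivity analysis fills that gap.

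**2. The plan's own figure.** 90,000 × 3.5 + 4,600 = 319,600, which reproduces. It says nothing about diagnosis mix or event rates, so everything below rests on assumptions.

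**3. Cardiac outcome, no true COVID-19 effect.** Assumed inputs:
- one-year risk of 2.5% in COVID-19 survivors and in comparators without an index event;
- recurrence risk r of 8%, 12% or 16% in comparators with one;
- share s of such patients among the comparators analysed;
- no COVID-19 patient with an index event.

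Comparator risk: p = s·r + (1 − s)·0.025. Apparent hazard ratio: ln(1 − 0.025) / ln(1 − p).

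Example, s = 5% and r = 16%: p = 0.05 × 0.16 + 0.95 × 0.025 = 0.03175, and HR = ln(0.975) / ln(0.96825) = 0.78.

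| Share s | r = 8% | r = 12% | r = 16% |
|---|---|---|---|
| 2% | 0.96 | 0.93 | 0.90 |
| 3% | 0.94 | 0.90 | 0.86 |
| 5% | 0.90 | 0.84 | 0.78 |
| 10% | 0.82 | 0.72 | 0.64 |

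**4. Would an interval exclude 1?** With 4,600 matched pairs there are 4,600 × 0.025 = 115 COVID-19 events, and SE(log HR) = √(1/115 + 1/(4,600p)), about 0.12 to 0.13. By the normal approximation at r = 12%, the 95% interval excludes 1 in about 9%, 14%, 29% and 76% of repetitions for s = 2%, 3%, 5% and 10%. At s = 5% and r = 8% it does so in about 13%. Here s is the share after matching.

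**5. Could a true excess be hidden?** At r = 12%, a true hazard ratio of 1.3 would appear as 1.3 × 0.838 = 1.09 at s = 5% and 1.3 × 0.721 = 0.94 at s = 10%.

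**6. If COVID-19 patients also carry the condition.** Let f be the share in comparators, g the share in COVID-19 patients and k the relative risk of a later admission. With no true effect the apparent risk ratio is [1 + g(k − 1)] / [1 + f(k − 1)]. For k = 5:
- f = 10%, g = 5%: 1.2/1.4 = 0.86
- f = g: 1.00
- f = 5%, g = 10%: 1.4/1.2 = 1.17

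The direction therefore depends on which cohort carries more index or in-stay events.

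**The case against.** **The protocol's lead contrast largely avoids this.** That is correct, and the pneumonia comparator is outside this point. The SAP does not define that cohort, however, so every contrast it sets up is exposed. The protocol's secondary comparators are exposed in any case.

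**A recurrence is a valid event.** The outcome is an emergency admission for the condition, not a first event, and the objective is a comparison with patients treated for other conditions. This stands for describing incidence, and it is why the whole-cohort result should stay. It does not settle the comparison: SAP 5.4.3 matches to remove confounding, and the SAP conclusion asks whether consequences differ from those of other ICU admissions.

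**The share after matching may be small.** Matching uses severity, ventilation, organ support, BMI and comorbidity, and eligibility is limited to general adult ICUs. This stands. At a 2-3% share and 12% recurrence the apparent hazard ratio is only 0.93-0.90.

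**A reader might infer that both contrasts must make COVID-19 look safer.** The documents do not support that. Both background sections report that venous thrombotic complications were fairly frequent in COVID-19 patients, and step 6 shows that this can cancel or reverse the bias. Cardiac complications are reported too, so even the cardiac direction is a likelihood, not a certainty.

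**The same logic reaches respiratory infection.** That outcome has the reverse problem, since the COVID-19 cohort has such an infection at index. The exclusion proposed here would empty that cohort, so it does not apply to that outcome.

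**Conclusion.** The point holds for the cardiac and venous thrombotic outcomes against the all-emergency cohorts: index diagnosis is an uncontrolled confounder, and Elixhauser history adjusts for it only in part. The cardiac contrast is likely to be biased towards making COVID-19 look safer; the direction for venous thrombosis is uncertain.

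The size is unknown. Under the assumptions in step 3 the apparent cardiac hazard ratio runs from 0.96 (2% share, 8% recurrence) to 0.64 (10% share, 16% recurrence). It moves towards or past 1 if COVID-19 patients carry in-stay events. A reader might take the larger figures as a forecast, but the documents give neither the shares nor the recurrence risks. The primary mortality outcome is not part of this point. The change should be made before analysis, because the plan as written would not show which way, or how far, these contrasts are shifted.

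**What to change.** In SAP 5.6, for the cardiac and venous thrombotic outcomes separately, pre-specify an analysis that:
- excludes, in every cohort including COVID-19, patients with that condition as the primary ICU diagnosis or coded during the index hospital stay;
- repeats the matching in the restricted set;
- is reported beside the whole-cohort result, which keeps the stated comparison with other conditions.

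The rule has to be symmetric. Excluding on primary ICU diagnosis alone would remove comparators admitted for pulmonary embolism but leave COVID-19 patients who had one during their stay.

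Base any statement that COVID-19 survivors have lower or higher cardiac or thrombotic risk on both results, and tabulate the index-diagnosis mix by cohort after matching.

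**Cost.** SAP wording, an extra match per outcome and comparator, somewhat fewer patients (including some with COVID-19), and a result that applies to survivors without the index event. The primary diagnosis is already used to define the cohorts in SAP 4.4.3 and 4.4.4. The team should confirm that index-stay coding is in the extract, because protocol 7.3 names only the windows before ICU admission and after hospital discharge.

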11.3. Sample Size Determination

The study size will be determined by the number of ICU survivors available from the CMP. The CMP currently holds around 10,000 patients admitted with confirmed COVID-19, of which ≈5,000 survived to hospital discharge. Of the survivors, we expected 90% (4,600) to have been admitted to an ICU in England or Wales.

Prior to the COVID-19 pandemic, there were around 130,000 emergency ICU admissions per annum in the CMP. Of these, around 100,000 survived to hospital discharge. We expect ≈90,000 to have been admitted to an ICU in England or Wales.

Study participants will include around 3.5 years of pre-pandemic admissions ($90,000 \times 3.5 = 315,000$) and 4,600 COVID admission during the pandemic giving a total sample size of 319,600.

11.4. Analysis populations

Primary group

Our primary group will be patients admitted with confirmed COVID-19 between 1st January to 1st July 2020.

Comparator groups

The primary comparator group will be patients admitted to ICU with viral or bacterial pneumonia between 1st July 2016 and 1st July 2019.

Secondary comparator groups will include:

- All emergency ICU admissions between 1st July 2016 and 1st July 2019
- All emergency ICU admissions between 1st July 2016 and 1st January 2020 where the primary diagnosis was not COVID-19
- All emergency ICU admissions between 1st January and 1st July 2020 where the primary diagnosis was not COVID-19

Pregnant patients

We will undertake a sub-group analysis in patients who were pregnant when treated for COVID-19 on ICU between 1st January and 1st July 2020.

11.5. Decision points

- March 2021: We will undertake data linkage and extraction from participating organisations. An interim analysis of outcomes at 180 days follow-up will be undertaken.
- October 2021: We will undertake data linkage and extraction from participating organisations. A final analysis of outcomes at 365 days follow-up will be undertaken.

